2.3.2. Safety Endpoints

Safety and tolerability will be assessed based on the incidence and severity of treatment emergent adverse events (AEs), serious adverse events (SAEs), vital signs, clinical laboratory results.

Specific safety sub-analyses will be performed to assess the safety of LB1148 in the following patient populations:

[figure not shown]
- patients who are on chemotherapy;
- patients with a venous port or catheter;
- patients with varicose veins and superficial vein thrombosis;
- patients with varying degrees of obesity;
- patients who are smokers;
- patients with varying degrees of renal function; and
- patient age groups, including 65-80 years old.

INVESTIGATIONAL PLAN

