4.3. Exclusion Criteria

Subjects will not be eligible for participation in the study if they meet ANY of the following exclusion criteria:

1. <18 or >80 years of age.
2. Requires emergency bowel surgery.
3. Has had 1 or more abdominal surgeries, excluding the current, for inflammatory bowel disease, including, but not limited to, inflammatory bowel disease (IBD), Crohn's Disease, or ulcerative colitis.

Note: This does not apply to previous surgery such as hernia repair unrelated to IBD.

4. American Society of Anesthesiologists (ASA) Class 4 or 5.
5. Known inability to take the study drug orally (i.e. complete small bowel obstruction).
6. Has contraindications or potential risk factors to taking TXA. These include subjects with:
 - a. Known sensitivity to TXA

- b. Recent craniotomy (past 30 days)
- c. Active cerebrovascular bleed
- d. Active thromboembolic disease (such as deep vein thrombosis, pulmonary embolism, cerebral thrombosis, ischemic stroke, or acute coronary syndrome)
- e. Acute promyelocytic leukemia taking all-trans retinoic acid for remission induction, or
- f. Continuing use of a combined hormonal contraceptive and or combined hormonal replacement therapy (including combined hormonal pill, patch, or vaginal ring)

7. Has peritoneal carcinomatosis.
8. History of or current seizure disorder.
9. Patients with myeloproliferative disorders.
10. Any other condition that, in the opinion of the Investigator, would preclude the subject from being an appropriate candidate for the study, including severe renal or hepatic impairment.
11. Planned treatment with alvimopan (Entereg®) during study participation period.
12. Planned use of 4% icodextrin (Adept®) or SEPRAFILM during the first surgery.
13. Received any other investigational therapy within 4 weeks prior to Randomization
14. Female subjects of childbearing potential with a positive urine or serum pregnancy test or who are not taking (or not willing to take) acceptable birth control measures (abstinence, intrauterine devices, contraceptive implants or barrier methods) through Day 30.
Additionally, those women who are lactating and insist on breast feeding within 5 days of the last dose of study drug.
15. Known history of radiation enteritis.

STUDY TREATMENTS

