7.15. Discontinuation or Withdrawal

The criteria for study entry and enrollment must be followed explicitly. If a subject who does not meet the study entry and enrollment criteria is inadvertently enrolled and study drug administration has been started, the Investigator should consult with the Sponsor or its designees regarding the termination or continuation of the study drug administration.

If study drug is discontinued, the subject will continue in the study and undergo all study assessments per the protocol in order to provide the follow-up data needed for the analysis of the entire intent-to-treat population. Investigator or delegated site personnel will make the effort to collect the necessary data per protocol; however, if the subject is to be completely off the study per the discretion of the subject, Investigator, or Sponsor, study procedures for Early Termination should be completed.

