10.7. Protocol Deviations

Sites are responsible for abiding by their IRB rules and regulations for reporting protocol deviations. Additionally, the following important protocol deviations will be reported to the Sponsor:

- Subject did not meet study eligibility criteria
- Subject did not receive the correct treatment assignment
- Subject received the wrong amount of a dose IP (i.e., $\pm 20\%$ of assigned dose)
- Subject received a prohibited concomitant medication
- Subject was not assessed for intra-abdominal adhesions

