Appendix 6 American Society of Anesthesiologists Classification System

The ASA Physical Status Classification System was last approved by the ASA House of Delegates on 15 October 2014.

ASA PS Classification	Definition	Examples, including but not limited to:
ASA I	A normal healthy patient.	Healthy, non-smoking, no or minimal alcohol use.
ASA II	A patient with mild systemic disease.	Mild diseases only without substantive functional limitations. Examples: current smoker, social alcohol drinker, pregnancy, obesity ($30 < \text{BMI} < 40$), well controlled DM/HTN, mild lung disease.
ASA III	A patient with severe systemic disease.	Substantive functional limitations; One or more moderate to severe diseases. Examples: poorly controlled DM or HTN, COPD, morbid obesity ($\text{BMI} \geq 40$), active hepatitis, alcohol dependence or abuse, implanted pacemaker, moderate reduction of ejection fraction, ESRD undergoing regularly scheduled dialysis, premature infant post-conceptional age < 60 weeks, history (> 3 months) of MI, CVA, TIA, or CAD/stents.
ASA IV	A patient with severe systemic disease that is a constant threat to life.	Examples: recent (< 3 months) MI, CVA, TIA, or CAD/stents, ongoing cardiac ischemia or severe valve dysfunction, severe reduction of ejection fraction, sepsis, DIC, ARD or ESRD not undergoing regularly scheduled dialysis.
ASA V	A moribund patient who is not expected to survive without the operation.	Examples: ruptured abdominal/thoracic aneurysm; massive trauma; intracranial bleed with mass effect; ischemic bowel in the face of significant cardiac pathology or multiple organ/system dysfunction.
ASA VI	A declared brain-dead patient whose organs are being removed for donor purposes.	

Abbreviations: ARD = advanced renal disease; BMI = body mass index; CAD = coronary artery disease; COPD = chronic obstructive pulmonary disease; CVA = cerebrovascular accident; DIC = disseminated intravascular coagulation; DM= diabetes mellitus; ESRD = end stage renal disease; HTN = hypertension; MI = myocardial infarction; TIA = transient ischemic attack.

*The addition of “E” denotes Emergency surgery: An emergency is defined as existing when delay in treatment of the patient would lead to a significant increase in the threat to life or body part.

Source: [ASA website](#).

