4 GENERAL METHODS

4.1 Analysis Populations

Due to coronavirus disease 2019 (COVID-19), some subjects enrolled and randomized prior to 01Jan2022 were released from the hospital prior to achieving GI2. In addition, subjects were randomized based on whether the surgery was to include a stoma or not and a subject was considered completed at Study Day 30, e.g., the second surgery was optional. Protocol Amendment 5 and 6 require subjects to have a stoma during the first surgery and require the second surgery for the subjects to be considered complete. The primary endpoint is now comparing the change from baseline in extent and severity of intra-abdominal adhesions rather than GI2 among subjects treated with LB1148 or placebo. These circumstances and changes require corresponding updates to the populations defined in the Study Protocol.

The **modified Intent-to-Treat (mITT)** population includes all randomized subjects who received any investigational test article on or after 01Jan2022, where subjects will be analyzed according to the treatment to which they were randomized.

Safety Population: The safety population will be defined as all subjects who receive any amount of investigational test article. Subjects will be analyzed according to the treatment actually received.

The **Per Protocol Population (PP)** includes subjects in the mITT population who met all inclusion and no exclusion criteria, received the complete appropriate study dose, and had no important protocol deviations or violations, where subjects will be analyzed according to the treatment to which they were randomized.

Study subjects may be replaced if found to be ineligible (violation of one or more inclusion/exclusion criteria), or if following randomization, did not go on to receive ANY amount of investigational test article.

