12 SAFETY ANALYSIS

12.1 Adverse Events

All adverse events will be coded using the Medical Dictionary for Regulatory Activities (MedDRA) coding system (Version 25.0). Frequency tables will be presented by treatment group for all adverse events (AEs) by system organ class and preferred term for the safety population. Frequency tables will also be presented for AEs leading to discontinuation of test article, AEs by maximum severity (per CTCAE Version 5.0 Section 7.11 Study Protocol), AEs related to test article, and serious AEs. Subject listings of all AEs will also be provided for the safety population.

In all displays, adverse events will be displayed by MedDRA System Organ Class (SOC) and Preferred Terms. Subjects who have the same AE occur more than once will be counted only once for that event. Subjects who have more than one AE within a system organ class will be counted only once in that system organ class. (The addition of severity or relatedness follow the same pattern.)

In addition, frequency tables by treatment group for all AEs by system organ class and preferred term will be presented for the following populations:

- Patients who have had chemotherapy in the last 60 days
- Patients with a venous port or catheter
- Patients with varicose veins and superficial vein thrombosis
- Patients with varying degrees of obesity
 - Baseline BMI 30-35
 - Baseline BMI 35-40
- Patients who are smokers
- Patients with varying degrees of renal function

- Baseline eGFR 45-59
- Baseline eGFR 30-44
- Baseline eGFR 15-29
- Baseline eGFR < 15
- Patient age groups
 - 18-64 years
 - 65-80 years

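### The SAP's adverse event tables by degree of obesity stop at BMI 40, although the current protocol sets no BMI limit

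*SAP*

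**What the plan says.** Protocol 2.3.2 (and the synopsis) commits the trial to safety sub-analyses in several named populations, one of them "patients with varying degrees of obesity". It sets no bands and no upper BMI bound.

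SAP 12.1 turns this list into adverse event frequency tables by treatment group. Under obesity it names two bands: BMI 30-35 and "Baseline BMI 35-40". Under renal function it names four eGFR bands, the last of them open-ended: "Baseline eGFR < 15". Under age it names 18-64 and 65-80 years.

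On eligibility, protocol 4.3 has 15 exclusion criteria and none mentions BMI. The nearest is "American Society of Anesthesiologists (ASA) Class 4 or 5". Appendix 6 puts a BMI of 40 or above under ASA III, in a list of examples that includes "poorly controlled DM or HTN, COPD, morbid obesity". ASA III is not excluded.

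On who is analyzed, SAP 4.1 states: "The safety population will be defined as all subjects who receive any amount of investigational test article".

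**The concern.** The SAP's obesity bands end at a BMI that the protocol does not treat as a limit. Followed as written, the sub-analysis leaves out the most obese subjects the trial may enroll.

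The omission matters more for this drug than it might for another. Protocol 7.3 makes thrombotic events an adverse event of special interest, protocol 7.4 notes a possible association between tranexamic acid and thrombosis in nonclinical data, and the Caprini form in Appendix 8 scores obesity as a risk factor for venous thromboembolism. The highest degree of obesity is a natural place to look for a safety signal, and it is the one degree without a table.

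The two bands also share an endpoint, so a subject at BMI 35 would be counted twice or assigned by a programmer's choice.

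**Working it through.** No sample size, power or error rate bears on this point. The check compares the BMI range that the SAP tables cover with the range that the protocol admits.

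**1. Range covered by SAP 12.1.** Read as closed intervals, the bands are [30, 35] and [35, 40].

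- Union: [30, 40].
- Intersection: {35}.
- Obese subjects in no band: BMI > 40. A BMI of exactly 40 is covered.

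**2. Range admitted by the protocol.** Of the 15 criteria in protocol 4.3, 0 limit BMI. Criterion 4 bars only ASA classes 4 and 5, and Appendix 6 lists a BMI of 40 or above under ASA III. Criterion 10 lets the investigator exclude a subject for any condition judged unsuitable, but that is discretion and not a BMI limit. The admitted obese range is therefore [30, ∞).

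**3. Gap.** [30, ∞) minus [30, 40] leaves BMI > 40. Because the safety population is everyone dosed, any such subject who takes study drug belongs in the adverse event analyses but in no obesity table.

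**4. Comparison with the other graded lists in SAP 12.1.** The renal list runs to an open extreme, although criterion 10 names severe renal impairment as a ground for exclusion in the investigator's opinion. The age bands together span the eligible range of 18 to 80 years. Only the obesity list stops short of what the protocol admits.

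**5. Possible origin.** The amendment summary (protocol Appendix 9) shows that an exclusion of BMI above 40 came in with Amendment 2 and was removed by Amendment 6, dated 26 August 2022. SAP 17 says version 2.0 (11 October 2022) reflects Amendments 4, 5 and 6, and version 3.0 followed on 10 March 2023. The upper edge of 40 equals the removed limit, and the SAP gives no other reason for it. This is history only; steps 1 to 3 rest on current text.

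**6. Number of tables.** Counting one table per listed subgroup or band: chemotherapy 1 + port or catheter 1 + varicose veins 1 + obesity 2 + smokers 1 + renal 4 + age 2 = 12. None is for BMI above 40. The SAP does not state a table count; bands could equally be columns of one table.

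**7. Coverage after the fix.** Bands [30, 35), [35, 40) and [40, ∞) have union [30, ∞) and no overlap. On the same count, 12 tables become 13.

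**The case against.** The case against giving this much weight has several parts.

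- **The information is largely available elsewhere.** SAP 6 gives the maximum BMI by treatment group for the safety population, and SAP 12.1 and 13 provide listings of adverse events and all collected data. If only a handful of subjects exceed BMI 40, their events can be read by subject and arm. This stands, and it is why the point is minor. A reader would still have to assemble by hand what the protocol says will be analyzed.
- **Few subjects can be affected.** SAP 4.3 plans up to 40 subjects for the adhesion endpoint, expected to give at least 30 randomized. The BMI exclusion was lifted only by Amendment 6, well after the cohort's start on 01Jan2022. Subjects eligible above BMI 40 can come only from the later part of that cohort. This is fair and bounds the eligible group.
- **Subjects dosed in breach of the former limit are hypothetical.** Protocol 7.15 does provide for the case: "If a subject who does not meet the study entry and enrollment criteria is inadvertently enrolled and study drug administration has been started". Protocol 10.7 lists among its important deviations "Subject did not meet study eligibility criteria". Such subjects would be in the safety population. But a subject over 80 dosed in breach would likewise fall in no age table, so this argument is secondary. The conclusion holds without it.
- **The protocol names no bands and leaves statistical detail to the SAP.** So this is incomplete coverage and not a contradiction. That is correct, but the SAP did choose explicit bands, and they omit a degree of obesity that the protocol admits.
- **Forty is also the boundary in the ASA appendix.** The documents do not prove that the band edge is a leftover from the old exclusion. The gap exists whatever its origin.

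**Conclusion.** The concern holds. SAP 12.1 has no obesity table for BMI above 40, the current protocol has no BMI limit, and protocol 2.3.2 requires a safety sub-analysis by degree of obesity. The overlap at exactly 35 is a separate, smaller defect.

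The consequence is minor, but it should be corrected. No test, decision rule or population changes, and the subjects concerned remain in the overall adverse event tables, an age-group table (if aged 18 to 80) and the listings. The number affected cannot be derived from the documents and may be zero. The conclusion assumes only that the bands are programmed as written and that the current eligibility criteria apply.

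**What to change.** In SAP 12.1, restate the obesity bands as BMI 30 to <35, 35 to <40, and 40 or above. Every BMI of 30 or more then falls in exactly one band. The cut at 40 follows the boundary in protocol Appendix 6, so a BMI of exactly 40 moves from the middle band to the top one.

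The cost is SAP wording and one more descriptive table. No new data are needed, because BMI is recorded at Screening (protocol Appendix 1, footnote 7). The drawback is that the added table will be sparse and may be empty. Fixing the bands in the SAP avoids choosing a cut after the data have been seen.

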⁵ Document any changes to subject's condition that affect inclusion/exclusion criteria. Subject must meet all inclusion/exclusion criteria at time of the surgery. As part of medical history review, Caprini risk factor score will be calculated and tobacco use recorded.

⁶ Concomitant medications taken within 14 days of randomization will be recorded during the Screening visit and through Post-Operative Day14 or Hospital Discharge or Study Termination (whichever comes first).

⁷ Screening physical exam includes weight measurement and height measurements, lower extremity assessment to identify any clinical symptoms of VTE, assessment of venous port or venous catheter, varicose veins, superficial vein thrombosis, and BMI. Focused examinations include lower extremity assessment to identify any clinical symptoms of VTE and weight measurements from Day 0 through Post-Operative Days 14 until Hospital Discharge or Study Termination (whichever comes first).

⁸ For data capture, use the vital signs (BP - systolic and diastolic measurements, HR, RR, oxygen saturation, and temperature) taken the closest to 0800 during the Surgical and Post-Surgical periods. For the re-operation Adhesion Evaluation, vitals should be recorded prior to surgery.

⁹ The study drug (a total of 700 mL) is administered orally prior to surgery as a split dose. For the first study drug administration, subjects will consume 350 mL (at any rate of consumption) 6-10 hours prior to surgery. The second study drug administration, subject will consume the remaining 350 mL (at any rate of consumption) 2-6 hours prior to surgery. Note: There is no co-administration of food or drink with the study drug. Eating, bowel preparation, and drinking should be withheld 1 hour before and 1 hour after study drug administration.

¹⁰ Please refer to [Section 9.4](#) for information regarding possible changes to the study after interim analysis evaluation.

¹¹ Capture all perioperative items the subject was given or consumed, including but not limited to, mechanical bowel prep, nutritional supplements, carbohydrate drinks, opioids, and analgesia.

¹² For flatus and stool, record the first noted event; if subject experiences POI, record the next event of flatus, and/or stool until resolution. Diet changes (liquid, solid, NPO) will be monitored.

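### SAP 12.1 gives renal safety tables only below eGFR 60, so subjects with normal or mildly reduced renal function have no table

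*SAP*

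**What the plan says.** Protocol 2.3.2 makes the commitment in firm terms: "Specific safety sub-analyses will be performed to assess the safety of LB1148 in the following patient populations". The list that follows includes "patients with varying degrees of renal function", with no upper or lower limit. The synopsis repeats it.

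SAP 12.1 turns each listed population into adverse event frequency tables by treatment group in the safety population. For renal function it names four bands: "Baseline eGFR 45-59", "Baseline eGFR 30-44", "Baseline eGFR 15-29" and baseline eGFR below 15. No renal band at 60 or above appears there or elsewhere in the SAP. In the same list, age is split into 18-64 and 65-80 years.

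Exclusion criterion 10 in Protocol 4.3 leaves to the Investigator's opinion any condition that makes a subject unsuitable, "including severe renal or hepatic impairment". It gives no eGFR threshold. Protocol Appendix 2 lists creatinine among the laboratory tests but not eGFR, and the SAP names no estimating equation.

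On a related wording point, the protocol and SAP both define one subgroup by varicose veins and superficial vein thrombosis. Footnote 7 of Protocol Appendix 1 lists the screening findings as separate items: "assessment of venous port or venous catheter, varicose veins, superficial vein thrombosis, and BMI".

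**The concern.** A sub-analysis over degrees of renal function should cover the degrees that the trial enrols. As written, it starts at moderately reduced function and goes down. The eligibility criteria steer severe impairment out and place no restriction on normal or mildly reduced function, yet that upper part of the range has no table.

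Two things are lost. First, mild impairment, which is itself a degree of renal function, cannot be examined. Second, a reader who sees more adverse events on LB1148 than on placebo in the 45-59 band cannot set that difference beside the same difference in subjects with better function. The tables therefore cannot show whether any excess is particular to reduced function or general.

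**Working it through.** No sample size, power or error-rate figure is involved, and the plan states no figure to reproduce. The check compares the bands with the commitment and with the eligibility criteria.

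**1. Coverage of the bands.** The upper limit of the highest band is 59.
- Bands at or below 59: 4 of 4.
- Bands at 60 or above: 0 of 4.
- For comparison, eligible ages run from 18 to 80, and the SAP's age groups (18-64 and 65-80) cover that whole range.

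I take mild reduction as eGFR 60-89 and normal function as 90 or above. These limits are an assumption, since the documents do not define them. The count of zero bands at 60 or above does not depend on where that split falls.

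**2. What subtraction can recover.** SAP 12.1 counts a subject once per preferred term, and the bands do not overlap, so counts add across them. For each arm and preferred term:

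overall count − (count in 45-59 + count in 30-44 + count in 15-29 + count below 15) = count in 60-89 + count in 90 or above + count with no calculable eGFR

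The left side is known from the planned tables. The right side has three unknowns and one equation. Subtraction therefore gives one pooled group and cannot isolate mild impairment or missing values. The same holds for the denominators.

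**3. Overlap with exclusion criterion 10.** The criterion has no cut-off, so the overlap depends on what severe is taken to mean.
- If severe means eGFR below 30: 2 of 4 bands (15-29 and below 15).
- If severe means eGFR below 15: 1 of 4 bands.

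The criterion also rests on judgement. Criterion 4 excludes ASA Class 4 or 5, and Protocol Appendix 6 gives end-stage renal disease on regular dialysis as an ASA III example, so criterion 4 alone does not remove such subjects. The low bands may be sparse, but the documents do not make them empty.

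**4. Number of subjects.** Neither document gives an eGFR distribution, so subjects per band, or outside all bands, cannot be computed.

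**5. Deriving eGFR.** Creatinine is collected at Screening, and SAP section 6 includes age and sex among the demographic data. The inputs exist, but different equations can place the same subject in different bands. Band membership is therefore not fixed until an equation is named.

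**The case against.** The strongest defence is that the protocol asks only for safety to be assessed in the listed populations. It does not ask whether the difference between LB1148 and placebo changes with renal function. Every band is tabulated by treatment group and so has its own placebo column, and an overall adverse event table exists. Adverse events and laboratory results are also listed by subject, so anyone can regroup later. All of this is descriptive, in a proof-of-concept study with nominal p-values.

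Much of that stands. A reader might infer that the renal tables have no comparator; they do, within each band. What is missing is a group at 60 or above. It also stands that no data are lost. But the protocol's phrase names a range of function, not impaired patients alone, so mild reduction falls within the request even on the narrow reading. Regrouping from listings after unblinding is weaker than bands fixed beforehand.

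A reader might also infer that two of the four bands are wasted on excluded subjects. That assumes a cut-off of eGFR 30, which the documents never give.

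A reader might further ask for matching tables of non-smokers and of subjects without a port or catheter. The protocol names only smokers and subjects with a port or catheter, and the SAP tabulates those. For a single yes/no factor the complement follows by subtraction, apart from missing values, so the extra tables are a preference.

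Finally, the vein wording might be read as a SAP departure. The SAP repeats the protocol's wording, so it is an ambiguity common to both documents.

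**Conclusion.** The concern holds in this form: the renal sub-analysis promised in Protocol 2.3.2 is only partly carried out, because none of the four bands in SAP 12.1 covers eGFR 60 or above and subtraction cannot recover mild impairment. This follows from the text under any eGFR distribution. Its size in subjects is unknown.

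The consequence is limited to descriptive safety tables; no efficacy result, test or error rate changes. Keeping bands below 30 is not an error, although they are likely to be sparse. The conclusion rests on one reading, that normal and mildly reduced function count among the varying degrees the protocol refers to.

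**What to change.** In SAP 12.1:

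- Add baseline eGFR bands 60-89 and 90 or above, by treatment group, beside 45-59 and 30-44.
- Collapse 15-29 and below 15 into below 30 if they prove sparse, so that nobody is dropped.
- Show n per arm for every band, and add a row for subjects whose eGFR is not calculable.
- Name the equation used to derive eGFR from the collected creatinine.
- As a minor clarification, state whether the vein subgroup means either condition or both.

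The cost is a few more descriptive tables and somewhat longer output. The creatinine and vein findings are already collected, so no new data are needed.
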